  - Total bilirubin  $> 2 \times$  ULN regardless of the level of AST/ALT
14. Resting QT interval corrected by Fridericia's formula (QTcF)  $> 450$  ms at screening
  15. Creatinine  $> 2 \times$  ULN in the absence of dehydration. In case of dehydration, creatinine should be  $< 2 \times$  ULN after oral/parenteral rehydration
  16. Any severe disease condition which might prohibit participation in this study
  17. Known chronic underlying disease such as sickle cell disease, and severe cardiac, renal, or hepatic impairment
  18. Known active or uncontrolled thyroid disease
  19. Inability to swallow oral medication (in tablet and/or liquid form)
  20. Patients with prior antimalarial therapy or antibiotics with antimalarial activity within minimum of their five (5) plasma half-lives (or within 4 weeks of screening if half-life is unknown)
  21. Use of other investigational drugs within 30 days of dosing or until the expected pharmacodynamic effect has returned to baseline, whichever is longer
  22. Patients taking medications prohibited by the protocol
  23. Previous participation in any malaria vaccine study or received malaria vaccine in any other circumstance within 3 months of dosing
  24. History or family history of long QT syndrome or sudden cardiac death, or any other clinical condition known to prolong the QTc interval, such as history of symptomatic cardiac arrhythmias, clinically relevant bradycardia or severe heart disease
  25. Use of agents known to prolong the QT interval unless it can be permanently discontinued for the duration of study
  26. History of hypersensitivity to any of the study drugs or its excipients or to drugs of similar chemical classes

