##### **6.2.1 Concomitant therapy**

Prior medications are defined as drugs taken and stopped prior to the first dose of study medication.

Concomitant medication is defined as any medication, other than the Investigational Medicinal Product (IMP), which is given at least once between the day of first dose of study medication and the last day of study visit (including those which were started pre-baseline and continued into the treatment period or follow-up period), including prescription and over-the-counter medicines, and any traditional or herbal remedies.

Paracetamol as an antipyretic, and metopimazine for repeated vomiting (or if not available, any other antiemetic which is not known to prolong QT and/or cause torsade de pointes) will be allowed. If paracetamol or equivalent drug is given as an antipyretic up to 72 hours prior to the first dose, it has to be reported as prior medication.

Metoclopramide is contraindicated from the period prior to the first dose to Day 5 post-dose (120 hours).

Beta-lactam antibiotics can be given in case of a bacterial infection appearing after enrolment. All antibiotics, new-quinolones included, with anti-malarial activity should be prohibited.

The investigator must instruct the patient (or parent/legal guardian) to notify the study site about any new medications he/she takes after the patient was enrolled into the study. All medications, procedures and significant non-drug therapies (including physical therapy and blood

transfusions) administered after the patient was enrolled into the study must be recorded in the concomitant medications eCRF.

Each concomitant drug must be individually assessed against all exclusion criteria/prohibited medication. If in doubt the investigator should contact the Novartis medical monitor before randomizing a patient or before allowing a new medication to be started.

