## 6.2.2 Prohibited medication

### Drug with potential impact on efficacy & safety:

- **Drugs with antimalarial effect:** Drugs/supplements which are known to have antimalarial effects are NOT allowed within minimum of their five (5) plasma half-lives (or minimum of 4 weeks if half-life is unknown) prior to enrollment and during the entire study period. They may be used in the course of managing a patient who has developed ETF or late treatment failure or failed to respond to standard-of-care. Lumefantrine-including treatments should be avoided as therapy for ETF, unless there is no alternative.
- **Drugs with QTc Potential:** Drugs/supplements which have potential to increase QTc interval such as but not limited to antiarrhythmic drugs, neuroleptics and antidepressant agents, metoclopramide, macrolides and fluoroquinolones antibiotics, imidazole and triazole antifungal agents, certain non-sedating antihistamines (terfenadine, astemizole), and cisapride, should be avoided during the study and within minimum of their five (5) plasma half-lives of last dose (or minimum of 14 days if unknown ) prior to dosing. Furthermore, drugs that slow the heart rate (HR), like digitalis and beta blockers should be avoided.
- **Drugs with potential liver safety concerns:** Drugs which are known to have potential hepatotoxicity should not be used during study and within minimum of their five (5) plasma half-lives of last dose (or minimum of 14 days if half-life is unknown) prior to dosing. This includes NSAIDs (also over-the-counter medicines) and herbal medicines. *Paracetamol < 4g/day (or equivalent pediatric dosage; 10 to 15 mg/kg orally every 4 to 6 hours) may be used however, exact doses and time should be recorded appropriately.*

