**Table 6-5 Prohibited Medications**

CYP Enzymes/transporter	Sensitive substrates a	Substrates with narrow therapeutic range b
CYP2D6	Atomoxetine, desipramine, dextromethorphan, metoprolol, nebivolol, perphenazine, tolterodine, venlafaxine	Thioridazine, neuroleptics, flecainide, metoprolol, and tricyclic antidepressants such as imipramine, amitriptyline, clomipramine
CYP3A	Alfentanil, aprepitant, budesonide, buspirone, conivaptan, darifenacin, darunavir, dasatinib, dronedarone, eletriptan, eplerenone, everolimus, felodipine, indinavir, fluticasone, lopinavir, lovastatin, lurasidone, maraviroc, midazolam, nisoldipine, quetiapine, saquinavir, sildenafil, simvastatin, sirolimus, tolvaptan, tipranavir, triazolam, vardenafil	Alfentanil, astemizole, cisapride, cyclosporine, dihydroergotamine, ergotamine, fentanyl, pimozide, quinidine, sirolimus, tacrolimus, terfenadine
CYP2B6c	Bupropion, efavirenz	
CYP2C8	Repaglinide d	Paclitaxel
CYP2C9	Celecoxib	Warfarin, phenytoin
OATP1B1	Bosentan, pravastatin	
a Sensitive CYP substrates refers to drugs whose plasma area under the curve (AUC) values have been shown to increase 5-fold or higher when co-administered with a known CYP inhibitor. b CYP substrates with narrow therapeutic range refers to drugs whose exposure-response relationship indicates that small increases in their exposure levels by the concomitant use of CYP inhibitors may lead to serious safety concerns (e.g., Torsades de Pointes). c The AUC of these substrates were not increased by 5-fold or more with a CYP2B6 inhibitor, but they represent the most sensitive substrates studied with available inhibitors evaluated to date. d Repaglinide is also a substrate for OATP1B1, and KAF156 potentially inhibits therapeutic OATP1B1 as well.		

Except for medication which may be required to treat adverse events, no new medication other than study drugs will be allowed from the first dosing until up to completion of Day 7 evaluations.

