2.4.2 Prior, concomitant and post therapies

Prior and concomitant medications will be summarized in separate tables by treatment group.

Concomitant rescue and other anti-malarial medications will also be summarized by treatment group.

Note – rescue medications and non-study antimalarial drugs are the same. If they are used after discontinuation of study drug due to early treatment failure, late clinical failure or late parasitological failure then they should be considered as rescue medications, otherwise, they are considered as other non-study drug antimalarial medications. Rescue medications will be

captured along with other concomitant medications by the investigators under rescue medication category.

Prior medications are defined as drugs taken and stopped prior to first dose of study medication. Any medication given at least once between the day of first dose of study medication and the last day of study visit will be a concomitant medication, including those which were started pre-baseline and continued into the treatment period.

Prior and concomitant medications will be coded according to the latest version of WHO Drug Reference List dictionary which employs the ATC. The number and percentage of patients taking prior and concomitant medications will be summarized for each treatment by ATC class and preferred term (PT).

Number and percentages of the patients received prohibited prior and concomitant drugs will be summarized

Safety set will be used.

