AGENTS	L01EC	VEMURAFENIB
ANALGESICS/ PSYCHO-	N02CX	
LEPTICS/ ANXIOLYTICS/	N05BX	
ANTIDEPRESSANTS	N06AX	VENLAFAXINE
ANTINEOPLASTIC		
AGENTS	L01XH	VORINOSTAT

Note: Use ATC Code (4th level code - ATC4) and Preferred term (CMDECOD) for merging to get information about medications as we do not have 5th level code (ATC5) information in the database.

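### SAP Table 5-9 has no metoclopramide entry, so the planned count of patients on prohibited drugs would miss any use of it

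*SAP*

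**What the plan says.** Protocol 6.2.1 (Concomitant therapy) gives metoclopramide a sentence of its own: "Metoclopramide is contraindicated from the period prior to the first dose to Day 5 post-dose (120 hours").

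Protocol 6.2.2 (Prohibited medication) names it again in the bullet on drugs with QTc potential. In that bullet, "metoclopramide, macrolides and fluoroquinolones antibiotics, imidazole and triazole antifungal agents, certain non-sedating antihistamines (terfenadine, astemizole), and cisapride, should be avoided during the study". The same bullet adds a washout before dosing of five half-lives, or 14 days if the half-life is unknown.

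SAP 2.4.2 plans an output on such use in the Safety set: "Number and percentages of the patients received prohibited prior and concomitant drugs will be summarized". SAP Table 2-4 lists prior and concomitant use of other prohibited medications as a summary and a listing.

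SAP 5.3 (Prohibited medications) holds Table 5-9, in three categories: drug-drug interaction, liver enzyme elevation, and QT prolongation and proarrhythmia. The note under the table gives the matching rule: "Use ATC Code (4th level code - ATC4) and Preferred term (CMDECOD) for merging to get information about medications". The reason given is that the database does not hold fifth-level ATC codes.

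**The concern.** Any drug missing from Table 5-9 cannot be recognised as prohibited by a program that follows the note. Metoclopramide is restricted by name in two protocol sections, with QTc potential as the stated reason in one of them. Some use is plausible: the protocol provides for vomiting of study drug, replacement doses and antiemetic treatment.

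At stake is the accuracy of the prohibited-drug summary. A reader of the study report would take that table as the record of how well the QTc restrictions were kept. It would show no metoclopramide use whether or not there was any.

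**Working it through.** No figure in the plan is at issue, so the check is a comparison of texts followed by a short calculation of what one missed patient is worth.

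**Step 1. Is the drug restricted?** Yes, by name in protocol 6.2.1 and again in 6.2.2.

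**Step 2. Is it in Table 5-9?** The table was read row by row. Metoclopramide is in none of the three categories. The column layout is disturbed in the text available to us, but the drug name occurs nowhere in the table.

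**Step 3. Could another row catch it?** The note asks for ATC4 and preferred term together.

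| Nearest rows in Table 5-9 | Preferred term matches metoclopramide? | Caught under the note? |
|---|---|---|
| Cisapride (A03FA02, functional gastrointestinal disorders) | No | No, whatever the ATC4 code |
| Aprepitant, chlorpromazine, droperidol, ondansetron (antiemetic rows) | No | No |
| Class rows such as neuroleptics, NSAIDs, protease inhibitors | Not classes of antiemetic or gastrointestinal drugs | No |

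A program matching on ATC4 alone would flag every drug that shares cisapride's fourth-level code. The documents give no code for metoclopramide, and the note does not allow that shortcut.

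**Step 4. Was the omission deliberate?** Nothing says so. The SAP's revision log for June 2024 records that prohibited drugs were added with QTc prolongation particularly in mind, and SAP section 4 declares no change to the protocol-specified analyses.

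**Step 5. Is it the only gap against 6.2.2?** No. Digitalis is named there and has no row. Fluoroquinolones are named as a class, and ciprofloxacin is the only one listed. Macrolides and beta blockers are also restricted as classes, and only some members have rows.

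**Step 6. What does a missed patient do to the summary?** The count of patients with any prohibited drug falls by the number who took metoclopramide and no other listed drug. A patient who also took a listed drug is still counted, but the metoclopramide line is lost. SAP 2.14 has descriptive statistics by cohort, and Table 2-4 marks no pooled analysis for this output. Assume the planned sizes, 1:1 allocation, everyone in the Safety set, and display by treatment group:

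- Run-in: 24/2 = 12 per group; 1/12 = 8.3 percentage points per missed patient.
- Cohort 1: 140/2 = 70 per group; 1/70 = 1.4 points.
- Cohort 2: 80/2 = 40 per group; 1/40 = 2.5 points.

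The documents do not give the number of users, so the total undercount is unknown and may be zero.

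**Step 7. What else depends on the table?** Use would still appear in the general concomitant-medication tables (SAP 2.4.2) and the DMC output on concomitant medications (SAP Table 2-6). It would appear in the deviation tabulation (SAP 2.3.3) if recorded as a deviation. In SAP Table 5-14, the PPS exclusion for prohibited non-antimalarial drugs concerns effects on efficacy. Protocol 6.2.2 lists metoclopramide for its QTc potential.

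**The case against.** Four points can be made on the other side.

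First, SAP 2.4.2 does not cite Table 5-9, and the mock shells that govern the outputs are not available. This stands. The link is an inference from the section title, the merge note and the absence of any other list, so the conclusion has to be conditional.

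Second, the merge note cannot be literal for the whole table. Rows labelled with a class, such as NSAIDs, cannot match an individual drug's preferred term. This also stands, and it shows that some judgement will enter the programming. It does not help here, because no class row covers drugs of this kind.

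Third, the list in 6.2.2 is open-ended by its own words, and Table 5-9 gives only selected members of several classes. A reader might infer that the table reproduces the QTc bullet with metoclopramide alone dropped. The documents do not support that. Terfenadine, astemizole and cisapride, also named in the bullet, sit among the drug-drug interaction rows and match protocol Table 6-5, and there are other gaps. What sets metoclopramide apart is its separate contraindication in 6.2.1.

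Fourth, a reader might infer that 6.2.1 and 6.2.2 contradict each other, because one stops at 120 h and the other runs for the whole study. They do not. Section 6.2.1 does not permit the drug after 120 h, and both rules can be obeyed. The rest of the text favours the stricter one: "Each concomitant drug must be individually assessed against all exclusion criteria/prohibited medication", and the alternative antiemetic allowed is "any other antiemetic which is not known to prolong QT and/or cause torsade de pointes".

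**Conclusion.** The point holds and is minor. Table 5-9 lacks a drug that the protocol restricts by name in two sections. A summary programmed from the table as its note directs would leave out any metoclopramide use and could undercount patients with prohibited medication. This rests on one assumption, that the SAP 2.4.2 summary is built from Table 5-9.

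The size is unknown because the frequency of use is not given. Only one descriptive safety summary and its listing are affected. A reader might go further and infer that the use would go unseen or that the efficacy result is at risk. The documents support neither: use remains visible in the general medication tables and the DMC output, although not labelled as prohibited, and the primary analysis and PPS do not depend on this row.

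**What to change.** Add a metoclopramide row to the QT prolongation category of SAP Table 5-9, taking the ATC4 code and preferred term from the coding dictionary. Then check the table against every other drug and class named in protocol 6.2.2, starting with digitalis and the fluoroquinolones, and add what is missing. A reference to Table 5-9 in SAP 2.4.2 would remove the need to infer the link.

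The cost is one row, one check of the list and, if wanted, one cross-reference. No new data are needed, because concomitant medications are already recorded and coded.

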5.4 AEs coding/grading

Adverse events are coded using the Medical dictionary for regulatory activities (MedDRA) terminology. AEs are assessed by investigators according to the most current Common Terminology Criteria for Adverse Events (CTCAE) version 5.0

5.5 Laboratory parameters derivations

Grade categorization of lab values will be assigned programmatically as per NCI Common Terminology Criteria for Adverse Events (CTCAE) version 5.0 (specify version used in the RAP). The calculation of CTCAE grades will be based on the observed laboratory values only, clinical assessments will not be taken into account. The criteria to assign CTCAE grades are given in Novartis internal criteria for CTCAE grading of laboratory parameters. The latest available version of the document based on the underlying CTCAE version 5.0 at the time of analysis will be used.

A severity grade of 0 will be assigned for all non-missing lab values not graded as 1 or higher. Grade 5 will not be used. For laboratory tests that are graded for both low and high values, summaries will be done separately and labelled by direction, e.g., sodium will be summarized as hyponatremia and hypernatremia.

5.6 Computation of Blood Pressure Percentiles for Arbitrary Sex, Age, and Height

Below algorithm is described in the Appendix B of the following reference: The Fourth Report on Diagnosis, Evaluation and Treatment of High Blood Pressure in Children and Adolescents. Pediatrics 2004; 114; 555.

- To compute the systolic blood pressure (SBP) percentile of a boy whose age is y years and height = h inches with SBP = x mmHg:
 - Convert the height of h inches to a height Z-score relative to boys of the same age (as per data tables provided [Table 5-11](#) and [Table 5-12](#); this is denoted by Z_{ht} . For age < 2 years, age is recorded in the CRF with month as the unit and will be converted into year with 1 decimal, the corresponding height Z score can be calculated using months (see [Table 5-11](#)).
 - Compute the expected SBP (μ) for boys of age y years and height h inches given by

$$\mu = \alpha + \sum_{j=1}^4 \beta_j (y - 10)^j + \sum_{k=1}^4 \gamma_k (Z_{ht})^k$$

where, regression coefficients are given in the 3rd column of [Table 5-10](#).

- Then convert the boy's observed SBP (x) to a Z-score (Z_{BP}) given by

$$Z_{BP} = \frac{(x - \mu)}{\sigma}$$

where, σ is given in the 3rd column for standard deviation row of [Table 5-10](#).

- To convert the bp Z-score to a percentile (P), compute $P = \Phi(Z_{BP}) \times 100\%$
where $\Phi(Z) =$ area under a standard normal distribution to the left of Z .

- Likewise, to compute percentiles for SBP for girls, diastolic blood pressure (DBP) (K5) for boys, and DBP (K5) for girls, use the regression coefficients from the 4th, 5th, and 6th columns of [Table 5-10](#).

For example, a 12-year-old boy, with height at the 90th percentile for his age-sex group, has a height Z-score = 1.28, and his expected SBP (μ) is

$$\mu = 102.19768 + 1.82416 (2) + 0.12776 (2^2) + 0.00249 (2^3) - 0.00135 (2^4) + 2.73157 (1.28) - 0.19618 (1.28^2) - 0.04659 (1.28^3) + 0.00947 (1.28^4) = 109.46 \text{ mmHg.}$$

Table 5-10 Regression coefficients from Blood Pressure Regression Models

Regression Coefficients From Blood Pressure Regression Models*

Variable Name	Symbol	Systolic BP		Diastolic BP5	
		Male	Female	Male	Female
Intercept	α	102.19768	102.01027	61.01217	60.50510
Age					
Age-10	β_1	1.82416	1.94397	0.68314	1.01301
(Age-10) ²	β_2	0.12776	0.00598	-0.09835	0.01157
(Age-10) ³	β_3	0.00249	-0.00789	0.01711	0.00424
(Age-10) ⁴	β_4	-0.00135	-0.00059	0.00045	-0.00137
Normalized height					
Zht	γ^1	2.73157	2.03526	1.46993	1.16641
Zht ²	γ^2	-0.19618	0.02534	-0.07849	0.12795
Zht ³	γ^3	-0.04659	-0.01884	-0.03144	-0.03869
Zht ⁴	γ^4	0.00947	0.00121	0.00967	-0.00079
Standard deviation	σ	10.7128	10.4855	11.6032	10.9573
ρ^\dagger		0.4100	0.3824	0.2436	0.2598
n (persons)		32,161	31,066	24,057	23,443
n (visits)		42,074	41,017	29,182	28,794

BP, blood pressure; Diastolic BP5, diastolic measurement at Korotkoff 5.

* The coefficients were obtained from mixed-effects linear regression models.

† The value of ρ represents the correlation between BP measurements at different ages for the same child after correcting for age and Zht. This computation was necessary because some studies contributing to the childhood BP database provided BP at more than one age.

Computation of Z-score for height:

As per the recommendation from Centers for Disease Control and Prevention (CDC) use WHO growth charts for 0 to < 2 years of age and CDC growth charts for age ≥ 2 years. Accordingly, convert the given height into corresponding Z-score as per [Table 5-11](#) and [Table 5-12](#) given for the growth standards using the following formula.

$$Z_{ht} = \frac{\left(\frac{\text{height}}{\text{median}}\right)^L - 1}{L * S}$$

where, median, L, S (i.e. CV) are provided in the [Table 5-11](#) for age up to 2 years and in [Table 5-12](#) for age 2-20 years; height in centimeters.

Table 5-3 Table for WHO standard Length-for-age growth chart for age 0 to to 2 years

Month	L	Boy		Girl	
		Median (cm)	S (CV)	Median (cm)	S (CV)
0	1	49.8842	0.03795	49.1477	0.0379
1	1	54.7244	0.03557	53.6872	0.0364
2	1	58.4249	0.03424	57.0673	0.03568
3	1	61.4292	0.03328	59.8029	0.0352
4	1	63.886	0.03257	62.0899	0.03486
5	1	65.9026	0.03204	64.0301	0.03463
6	1	67.6236	0.03165	65.7311	0.03448
7	1	69.1645	0.03139	67.2873	0.03441
8	1	70.5994	0.03124	68.7498	0.0344
9	1	71.9687	0.03117	70.1435	0.03444
10	1	73.2812	0.03118	71.4818	0.03452
11	1	74.5388	0.03125	72.771	0.03464
12	1	75.7488	0.03137	74.015	0.03479
13	1	76.9186	0.03154	75.2176	0.03496
14	1	78.0497	0.03174	76.3817	0.03514
15	1	79.1458	0.03197	77.5099	0.03534
16	1	80.2113	0.03222	78.6055	0.03555
17	1	81.2487	0.0325	79.671	0.03576
18	1	82.2587	0.03279	80.7079	0.03598
19	1	83.2418	0.0331	81.7182	0.0362
20	1	84.1996	0.03342	82.7036	0.03643
21	1	85.1348	0.03376	83.6654	0.03666
22	1	86.0477	0.0341	84.604	0.03688
23	1	86.941	0.03445	85.5202	0.03711

Reference:

https://www.cdc.gov/growthcharts/who/boys_length_weight.htmhttps://www.cdc.gov/growthcharts/who/girls_length_weight.htm

Note – Table 5-11 to be accessed from the GPS II growth_data (where TEST='BODY LENGTH' and YEAR_CHG=WHO2006)

Table 5-12 Table for CDC growth standard height-for-age growth charts for age 2 - 20 years

Age(year)	Boy			Girl		
	L	Median (cm)	S (CV)	L	Median (cm)	S (CV)
2	0.941524	86.4522	0.040322	1.072449	84.97556	0.040791

3	-0.39092	95.27359	0.040534	0.541981	94.21336	0.042018
4	0.827637	102.5105	0.041344	0.225706	101.0339	0.04326
5	1.266367	109.1751	0.042593	-0.05773	107.9566	0.044277
6	1.137443	115.6609	0.043673	-0.21907	115.0055	0.044964
7	0.753244	122.0305	0.044403	-0.21021	121.7617	0.045461
8	0.455268	128.1237	0.045127	-0.07928	127.8263	0.045968
9	0.415687	133.7345	0.046217	0.084148	133.1304	0.046884
10	0.505564	138.8234	0.04761	0.284749	138.2112	0.048705
11	0.487939	143.7304	0.048938	0.74429	144.2609	0.050524
12	0.420919	149.3088	0.049948	1.303045	151.4866	0.048599
13	0.81624	156.4099	0.050333	1.242968	157.3437	0.043859
14	1.670433	164.1418	0.048945	0.956572	160.4777	0.041022
15	2.20518	170.1393	0.04589	0.89557	161.898	0.040084
16	2.113023	173.6101	0.043086	0.941146	162.569	0.039821
17	1.724738	175.341	0.041408	0.999506	162.9238	0.039732
18	1.399999	176.185	0.040644	1.047571	163.1308	0.039687
19	1.229163	176.6179	0.040391	1.083315	163.259	0.039657
20	1.167279	176.8492	0.04037	1.108046	163.3383	0.039636

Reference: <https://www.cdc.gov/growthcharts/data/zscore/statage.csv>

Note – Table 5-12 to be accessed from the GPSII growth_data (where TEST='HEIGHT' and YEAR_CHG=CDC2000)

